Patient's providers will first approach them to evaluate their willingness to participate in the study by providing the patient with a study information letter with an 'opt out' mechanism. Subjects will then be approached. Subjects will then be assessed for study eligibility as described above. Eligible and consenting patients who experience PPH will then be randomized to "control" or "ROTEM" groups by a computer generated randomization scheme. The obstetrician, nurse, and anesthesiologist involved in the cases will not be blinded to the study solution assignments. An investigator not involved in the case will conduct ROTEM measurements at any time standard coagulation labs are sent.

The management of PPH can occur in the OR or in the labor room. If a patient hemorrhages after vaginal delivery, we do occasionally draw a PPH lab panel [and study lab for a randomized patient] in the labor room. Many times, these patients are then transported to the operating room for further management. The ROTEM device is stationed between labor ORs 3 and 4. A patient sample in a blue vacutainer tube is taken to the ROTEM device from the labor room or the OR, by a co-investigator. At the time of hemorrhage recognition, a blue top and a purple top are drawn and sent to central lab (for any patient, in the study or not). Study patients have one additional blue top drawn for their ROTEM test. By collecting the study sample at the same time our routine samples are sent, study-specific intervention (new IV access solely for study purposes) is avoided. At maximum, we will draw less than 1 tablespoon extra blood for ROTEM® testing during the entire course of this research study. Patients will receive standard of

care for labor and delivery, cesarean delivery, and postpartum care. Patients admitted for delivery at Brigham and Women's Hospital have baseline labs drawn as standard of care. Baseline labs include: type and screen, serum hemoglobin, platelet count, fibrinogen, activated partial thromboplastin time (aPTT), prothrombin time (PT), and red top test.

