All clinical and other data obtained during this study will be considered confidential. Procedures to limit access to subject charts and information from the study will be in place. The names of study participants will be known only to the investigators. No information regarding the identity of individual subjects will be utilized for publications.

Outcomes considered serious adverse events including hemodynamic instability requiring epinephrine or norepinephrine or resulting in loss of consciousness or cardiovascular collapse, or allergic or anaphylactic reactions may all fit the criteria for withdrawal from the study. Each of these events will warrant an evaluation by the PI; please see “monitoring section” below.

Subject Costs

There will be no costs to the subjects related to the conduct of this study, as there are no additional medications or tests that are not already the routine standard of care at Brigham and Women’s Hospital. ROTEM testing used in the study group will be performed by qualified obstetric anesthesiology physicians under the supervision of a certified lab director, with funding from the department of Obstetrics and Gynecology. Otherwise, subjects and/or their insurance companies will be responsible for the routine medical and surgical procedures and care associated with their cesarean delivery or vaginal delivery and hospitalization.

BIOSTATISTICAL ANALYSIS

ROTEM values between the control and ROTEM groups will be compared as quantitative outcomes against pre-established ranges for each value in pregnancy and choice of product transfused with or without the ROTEM protocol will be compared.

Sample size calculations for the primary outcome of number of blood products transfused is based on a surrogate finding of reduction in transfused products in a matched study population that was demonstrable using 50 subjects per group). We anticipate that by recruiting the same number of patients as in this previous study (100 patients total), we will reproduce the effects of reducing blood product transfusion. A group size of $n = 50$ will give a power of 80% ($\beta = 0.2$) based on a 5% significance ($\alpha = 0.05$); 100 subjects per group will be recruited with the goal of completing 50 subjects in the control group and 50 subjects in the ROTEM group.

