Data will be analyzed using one-way analysis of variance and Kruskal-Wallis tests as appropriate. Analysis of variance will be used to compare intergroup demographic data, estimated blood loss (EBL), ROTEM values, and hemoglobin values. All statistical analyses will be performed using Statview v 5.0 for Macintosh. A P value < 0.05 will be considered significant and all data will be reported as mean \pm standard deviation.

Note: the study was stopped prior to our goal enrollment of 100 patients (N = 50 per group). Our total recruitment was N = 49; 26 control, 23 ROTEM due to slower than anticipated recruitment (3 years and 1 month). The decision to stop the trial early was not out of concern for patient safety or adverse events. We are aware that trials stopped earlier than anticipated may dramatically overestimate the effect of an intervention. However, given our lack of impact on our primary outcome in the intervention group we can infer that additional recruitment would yield results of the same clinical outcome (no effect).

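### Delivery mode is known before randomisation, yet neither the described allocation nor the planned comparison of product counts takes it into account

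*Combined protocol and SAP*

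**What the plan says.** The study title covers PPH after either mode of delivery. Under Study Procedures, eligible and consenting women who experience PPH are assigned to "groups by a computer generated randomization scheme"; no stratification factor or blocking is named. The same section notes that "The management of PPH can occur in the OR or in the labor room", and that women who bleed after vaginal delivery are often moved to the operating room. Of the equipment it says "The ROTEM device is stationed between labor ORs 3 and 4", and samples are taken to it from either setting.

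The primary endpoint is the number of blood products transfused from PPH diagnosis to 48 hours. Under Biostatistical Analysis the method is "Data will be analyzed using one-way analysis of variance and Kruskal-Wallis tests as appropriate". Demographics are also to be compared between arms, but that is not an adjustment, and mode is not mentioned there. No covariate, stratified test or by-mode table appears anywhere.

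The sample size is "based on a surrogate finding of reduction in transfused products in a matched study population", "with the goal of completing 50 subjects in the control group and 50 subjects in the ROTEM group". No mean difference, standard deviation (SD) or cesarean share is given. The closing note reports that recruitment stopped at 49 women (26 control, 23 ROTEM) and that no impact was seen on the primary outcome.

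**The concern.** Delivery mode may predict how many products a woman receives. If it does, a one-factor test gives up information that is available at almost no cost. The between-mode variation inflates the error term, and a chance difference in cesarean share between arms moves the observed difference in product count without the analysis recognising it. Both matter more in a small trial, and this one ended with about 25 women per arm.

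Mode is a proper adjustment factor here. PPH follows delivery and randomisation follows PPH, so mode is a baseline variable and adjusting for it cannot introduce post-randomisation bias.

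**Working it through.** **Inputs from the documents.** Planned 50 + 50; power 80%; significance 5% (sidedness not stated, two-sided assumed); achieved 26 + 23.

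**Inputs assumed.** Share of variance in product count explained by mode, R² = 0.01 to 0.20. Cesarean share, 40% to 71%. The documents give neither.

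**1. The plan's own figure.** It cannot be reproduced, because no effect or SD is stated. It can only be solved backwards. With the normal approximation, d = (1.960 + 0.842) × √(2/50) = 0.560. With the t-test, d = 0.566, which is used below.

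**2. Power after adjusting for mode.** Adjustment shrinks the residual SD by √(1 − R²), so the standardised effect becomes d/√(1 − R²). The equivalent gain in patients is 1/(1 − R²) − 1.

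| R² | adjusted d | power at 50/50 | power at 26/23 | equivalent extra patients |
|---|---|---|---|---|
| 0 (unadjusted) | 0.566 | 80.0% | 49.1% | – |
| 0.01 | 0.569 | 80.4% | 49.5% | 1% |
| 0.10 | 0.596 | 84.0% | 53.2% | 11% |
| 0.20 | 0.633 | 87.9% | 58.1% | 25% |

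**3. Chance of a mode imbalance under unstratified allocation.** With K cesareans in total, the number X in the first arm is hypergeometric. The probability required is P(|X/n₁ − (K − X)/n₂| ≥ 0.20).

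- At 26/23 with K = 25, the condition is met when X ≤ 10 or X ≥ 16, which has probability 0.156. For K = 20, 30 and 35 (41%, 61% and 71%) the values are 0.155, 0.142 and 0.125.
- At 50/50 with K = 50, it is met when X ≤ 20 or X ≥ 30, which has probability 0.071. For K = 40, 60 and 70 the values are 0.066, 0.066 and 0.049.

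**4. What a 20-point imbalance does.** Let m be the between-mode difference in within-mode SDs and p the cesarean share. Then R² = p(1 − p)m²/[1 + p(1 − p)m²], and the shift in the arm difference, in total SDs, is 0.20 × m × √(1 − R²). With p = 0.5:

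- R² = 0.01: m = 0.20, shift 0.04 SD, or 7% of d = 0.566.
- R² = 0.10: m = 0.67, shift 0.13 SD, or 22%.
- R² = 0.20: m = 1.00, shift 0.18 SD, or 32%.

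**5. Validity of the unadjusted test.** Negative binomial counts were simulated with no arm effect, half cesareans, a vaginal mean of 2 and a cesarean mean of 2, 4 or 6 (10,000 runs each, at 50/50 and 26/23). Rejection rates for one-way ANOVA and Kruskal-Wallis lay between 4.4% and 5.3%. The nominal 5% level holds.

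**The case against.** The strongest reply is that an unadjusted comparison of two randomised arms is valid, that chance imbalance is already part of its sampling error, and that the gain from adjustment rests wholly on assumptions. This stands. At R² = 0.01 the gain is under half a percentage point of power, and the documents cannot tell that case from R² = 0.20. Large imbalances are also the exception: at 26/23, a difference below 20 points is 84–88% likely. Stopping at 49 women costs far more power (80% to 49% at the implied effect) than mode adjustment could recover, and that is a separate matter.

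Three stronger readings are tempting but not supported:

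- *That the planned test is biased because it credits a mode difference to ROTEM.* Step 5 shows that the error rate is kept. The issue is precision and the make-up of the realised sample, not systematic bias.
- *That women with cesarean PPH get faster access to ROTEM results because the device is near the operating rooms.* Study Procedures says that a co-investigator takes the sample to the device from the labor room or the operating room. It records no delay and no difference in access by mode.
- *That the title promises an effect in each mode.* It names the population only. A different effect by mode would be an interaction, which an additive mode term would not address and which 49 women could estimate only very imprecisely.

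What the reply does not remove is that mode is a known baseline factor, and that using it costs almost nothing.

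**Conclusion.** The point holds as a missed gain in efficiency, not as a flaw in validity. The plan pools the two modes, describes no stratification and names only single-factor tests. Since the randomisation scheme is not detailed, the most that can be said is that no stratification is described.

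The benefit runs from negligible to about 8 percentage points of power at 50 per arm, or about 9 at 26/23. This depends on the assumed R² of 0.01 to 0.20, a two-sided test and an effect size solved backwards from the stated power. The imbalance probabilities depend on the assumed cesarean share. A reader might infer that adjustment could overturn the reported lack of effect. Nothing in the documents supports that: they give no result by mode, and even at R² = 0.20 power at 26/23 stays below 60%.

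**What to change.** State in Biostatistical Analysis that the comparison of product counts accounts for delivery mode, by a van Elteren (mode-stratified rank) test or by a count or two-factor model with arm and mode. Report product counts by arm within each mode, descriptively.

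The closing note shows that the primary result is already known. For the 49 women, therefore, present the mode-adjusted result as a labelled post hoc sensitivity analysis beside the planned test, not as a replacement for it. Allocation stratified by mode is relevant only to a restart or successor trial, which would need a separate list for each mode.

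The cost is one degree of freedom, a few lines of text and slight extra analysis work, using a factor known for every woman. No further patients or procedures are needed.

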Transfusion will be based on standard of care utilizing clinical criteria of hemodynamics (noninvasive blood pressure, heart rate, arterial line if deemed clinically useful) and coagulation labs (PT, aPTT, fibrinogen, complete blood count, red top test) in both groups. In addition to standard of care, additional ROTEM blood assays will be performed at any time routine coagulation labs are sent. Providers in the control group will be blinded to ROTEM results. Providers in the ROTEM group will receive real-time ROTEM results and a previously validated ROTEM-based transfusion algorithm for PPH (Mallaiah et al 2015). The investigator will quantitatively measure blood loss during the vaginal or cesarean delivery using a previously validated method (Triton System, Gauss Surgical Inc. Los Altos, CA). The total intravenous fluids given from start to conclusion of the study period will be recorded. The use of vasopressors, uterotonic agents, and antiemetic agents will be recorded.

Study Endpoints

Early Endpoints

Two definitions of early endpoints will be utilized:

1. Subject decision for withdrawal from participation at any time.
2. Any operative or medical condition changes prior to or during the entire study period deemed unacceptable by the obstetrician, anesthesiologist, or physician investigator.

Primary Endpoint

1. Number of blood products transfused, t_0 = diagnosis of PPH by criteria defined above; $t_{\text{final}} = 48\text{h}$ after onset of PPH.

Secondary Endpoints

1. ROTEM values drawn at the time of the last blood sampling within 4 hours from leaving the operating room or within 4 hours from the last blood transfusion, whichever occurs later.
2. Intraoperative blood loss (visual estimate in suction canister and sponges, EBL, and pre- vs post-delivery hemoglobin values).

Maternal morbidity: admission to the intensive care unit postpartum, need for additional postoperative procedures for bleeding, hysterectomy, postoperative infection, transfusion reaction, acute kidney injury, hypovolemic shock, vasopressor requirement, or mortality. Patient records at the 6-week postpartum visit will be reviewed for any incidence of delayed hemorrhage after hospital discharge.

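### The arms are compared without covariates although baseline coagulation values are collected: the tests are valid, but precision is given up, by an amount the documents do not let us fix

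*Combined protocol and SAP*

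**What the plan says.** **Analysis.** BIOSTATISTICAL ANALYSIS states: "Analysis of variance will be used to compare intergroup demographic data, estimated blood loss (EBL), ROTEM values, and hemoglobin values". The sentence before it offers one-way ANOVA or Kruskal-Wallis tests for the data in general, and that is the only method that can cover the primary endpoint. Neither sentence names a covariate. The threshold is "A P value < 0.05 will be considered significant". STUDY PROCEDURES describes a computer-generated randomization scheme and mentions no stratification.

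**Samples.** STUDY PROCEDURES lists routine admission labs, among them hemoglobin, platelets, fibrinogen, aPTT and PT. When hemorrhage is recognized, coagulation and blood count tubes go to the central lab for every patient, and "Study patients have one additional blue top drawn for their ROTEM test". ROTEM is run in both arms whenever coagulation labs are sent, with control providers blinded to the result.

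**Endpoints.** The primary endpoint is the number of blood products from diagnosis to 48 hours. The first secondary endpoint is "ROTEM values drawn at the time of the last blood sampling", within a 4-hour window. The nearest the plan comes to using a baseline is the second secondary endpoint, which lists hemoglobin before and after delivery as a measure of blood loss.

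**Size.** A group size of 50 "will give a power of 80" percent, with the "goal of completing 50 subjects in the control group and 50 subjects in the ROTEM group". The closing note reports: "Our total recruitment was N = 49; 26 control, 23 ROTEM".

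**The concern.** A woman's clot strength and fibrinogen before treatment plausibly predict her last ROTEM value and, perhaps less strongly, how many products she receives. If so, part of the spread in the outcome is explained by something already measured, and a test without that covariate treats it as noise. In a small trial without described stratification, the arms may also differ by chance in starting coagulation status. An unadjusted estimate carries that difference with it.

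What is at stake is the width of the interval and the accuracy of the estimate given the imbalance that occurred. This matters more because the closing note argues from 49 women that further recruitment would also have shown no effect. With enrollment closed, analysis is the only remaining source of precision.

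**Working it through.** **Step 1. The plan's own figure.** The 80% power at 50 per group cannot be reproduced, because no mean, SD or difference is stated; the sample size "is based on a surrogate finding of reduction in transfused products in a matched study population". Solving backwards, with two-sided 5% assumed because sidedness is not given:

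d = (1.960 + 0.842) × √(2/50) = 0.560 SD

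(0.566 with the t distribution; 0.497 if one-sided.) This is only the difference that the claim implies.

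**Step 2. Chance imbalance in a baseline value.** In baseline SDs, SE = √(1/n₁ + 1/n₂).

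- 26 vs 23: √(1/26 + 1/23) = 0.286. The 95% range is ±1.96 × 0.286 = ±0.56. P(|difference| > 0.2) = 49%; P(> 0.3) = 30%.
- 50 vs 50: √(2/50) = 0.200. The 95% range is ±0.39. The same probabilities are 32% and 13%.

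**Step 3. How much of it reaches the outcome.** In a linear model, an imbalance of b baseline SDs shifts the unadjusted outcome difference by ρ × b outcome SDs, where ρ is the baseline-to-outcome correlation. The documents give no ρ, so 0.2 to 0.7 is assumed.

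- b = 0.2: 0.06 to 0.14 SD for ρ = 0.3 to 0.7.
- b = 0.3: 0.09 to 0.21 SD.
- b = 0.56, the edge of the 95% range at 26 vs 23: 0.17, 0.28 or 0.39 SD for ρ = 0.3, 0.5 or 0.7.

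**Step 4. Precision from adjustment.** Residual variance is multiplied by 1 − ρ² and interval width by √(1 − ρ²). Power for the implied 0.560 SD is Φ(0.560 / (SE × √(1 − ρ²)) − 1.96). For example, at ρ = 0.5 and 26 vs 23: 0.560 / (0.286 × 0.866) = 2.26, and Φ(0.30) = 0.62.

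| Assumed ρ | 1 − ρ² | Interval narrower by | Information from 49 women, 49/(1 − ρ²) | Power, 50 vs 50 | Power, 26 vs 23 |
|---|---|---|---|---|---|
| 0 (unadjusted) | 1.00 | 0% | 49 | 80% | 50% |
| 0.2 | 0.96 | 2% | 51 | 82% | 52% |
| 0.3 | 0.91 | 5% | 54 | 84% | 54% |
| 0.5 | 0.75 | 13% | 65 | 90% | 62% |
| 0.7 | 0.51 | 29% | 96 | 98% | 78% |

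These are normal approximations for a linear model. At 26 vs 23 the t distribution gives slightly lower power (48% unadjusted; 60% adjusted at ρ = 0.5). They do not carry over to a skewed product count.

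**Step 5. Is the unadjusted test valid?** In 40,000 simulated null trials of 26 vs 23 for each of ρ = 0.3, 0.5 and 0.7, its overall type I error was 4.9% to 5.2%. Among the 16% of trials with a baseline imbalance above 0.4 SD, it was 7%, 13% and 19% respectively.

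**Step 6. When is the recognition sample drawn?** STUDY PROCEDURES randomizes after hemorrhage occurs but does not order randomization against the recognition draw. It also refers to a study lab for a patient already randomized, so the draw may come second. No ROTEM result can guide care before the first sample is run, but that does not make the sample pre-randomization. The admission labs precede the hemorrhage and therefore randomization.

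**The case against.** The strongest reply is that this is not an error. The unadjusted standard error already allows for chance imbalance, and overall type I error is 5%. A reader might infer that the planned tests are biased, or that the reported lack of effect reflects unequal starting coagulation. The documents support neither: Step 5 shows validity on average, and no baseline values by arm are given. The 49% and 30% are chances of a baseline difference, not of a wrong answer; imbalances of 0.2 or 0.3 SD shift the outcome by less than its standard error of 0.286 SD. All of this stands.

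Four further points also stand.

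- A reader might take the recognition sample as a true pre-randomization value. That is not documented, and care staff are unblinded, so if randomization comes first they could influence when the sample is drawn and what is given before it.
- The last ROTEM value often follows transfusion, which may correct abnormal results and weaken its correlation with the first. At 0.2 the gain is about 2% of interval width.
- The precision figures concern a linear ROTEM model, a secondary endpoint. They say nothing about the gain for product count.
- The result is known, so choosing covariates and models now adds flexibility.

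A reader might also conclude that recognition values go unused altogether. The plan compares ROTEM values without limiting them to the last sample, so those values may be compared between arms; they are simply not used as covariates.

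None of this removes the point that baseline values already collected are left out of every between-arm model.

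**Conclusion.** The concern holds as a matter of precision, not validity. The planned tests are sound on average. They forgo a gain that costs almost nothing, and they leave chance imbalance, with SE 0.286 SD at 26 vs 23 or 0.20 SD at 50 vs 50, in the estimate.

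For the last ROTEM value, adjustment would narrow the interval by between 2% and 29% over the assumed correlations of 0.2 to 0.7. The documents do not say where in that range the trial lies. The 78% power and the 96 women's worth of information sit at its favorable end and should not be read as expected gains. For product count the size of the gain is unknown.

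The power figures rest further on a two-sided test and on the 0.560 SD implied by the plan's own claim. Using the recognition sample as the covariate rests on its timing, which must be established first. Adjustment cannot by itself confirm or overturn the reported lack of effect.

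**What to change.** 1. **Last ROTEM value.** Add an ANCOVA on arm plus the same parameter from the recognition sample. State when that sample was drawn, and use it only if it preceded randomization or at least any ROTEM-guided treatment. Otherwise use admission fibrinogen or platelets.
2. **Women with one sample.** Their first and last values coincide, so the model would regress a value on itself. Either use the admission lab as covariate for all women, or exclude these women in a stated sensitivity analysis. Exclusion should stay a sensitivity analysis, because the number of samples is determined after hemorrhage management begins.
3. **48-hour product count.** Add one count regression, for example negative binomial, on arm with one fixed covariate, admission fibrinogen.
4. **Reporting.** Keep the planned unadjusted tests in place. Give the adjusted estimates with confidence intervals beside them, label them post hoc, and report them whichever way they point.

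The cost is one degree of freedom per model and a little programming, in software that fits these models; whether the package named in the plan does so should be checked. No new patient, visit or sample is needed.

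### The blood-loss comparison neither separates nor adjusts for loss before randomization, which costs precision on a secondary endpoint by an amount the documents do not fix

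*Combined protocol and SAP*

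**What the plan says.** All statements are in the combined protocol and SAP.

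- **BIOSTATISTICAL ANALYSIS, general rule:** "Data will be analyzed using one-way analysis of variance and Kruskal-Wallis tests as appropriate". No criterion says when each test applies.
- **Same section, next sentence:** "Analysis of variance will be used to compare intergroup demographic data, estimated blood loss (EBL), ROTEM values, and hemoglobin values". Blood loss is thus assigned to ANOVA by name, without a transformation or covariate. The section adds that "all data will be reported as mean" with standard deviation, which is the raw scale.
- **STUDY PROCEDURES, randomization:** "Eligible and consenting patients who experience PPH will then be randomized".
- **STUDY PROCEDURES, measurement:** "The investigator will quantitatively measure blood loss during the vaginal or cesarean delivery using a previously validated method".
- **Secondary Endpoints:** "Intraoperative blood loss (visual estimate in suction canister and sponges, EBL, and pre- vs post-delivery hemoglobin values". No start time is given. The primary endpoint does have one: "t_0 = diagnosis of PPH by criteria defined above".

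**The concern.** Randomization follows the hemorrhage, so some blood is already lost when the arm is assigned. A measurement that runs through the delivery will normally count that blood. ROTEM results cannot change it, yet its variation between women goes into the error term of a one-way ANOVA. A reading of cumulative loss at randomization, used as a covariate, would remove most of that variation.

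What is at stake is whether this secondary endpoint can show a real reduction in later bleeding, or exclude one. That matters more at the achieved 49 women (26 control, 23 ROTEM) than at the planned 50 per group, because a non-significant result is easily read as no effect.

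**Working it through.** **1. The plan's own figure.** The only stated power is 80% at 50 per group and 5% significance, for number of blood products. It has no effect size or SD, so it cannot be reproduced. It corresponds to a standardized difference of (1.96 + 0.84) × √(2/50) = 0.56, two-sided. At 26/23 that difference has about 50% power, since 0.56 / √(1/26 + 1/23) = 1.96. No power is stated for blood loss.

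**2. Inputs.** From the documents: ANOVA without covariate, randomization after PPH, group sizes 50/50 and 26/23, alpha 0.05 (two-sided assumed). Everything else is an assumption:
- loss before randomization lognormal, median 1000 mL, log-SD 0.35 (main) or 0.1 (women randomized at nearly the same loss);
- later loss lognormal, median 600 mL, log-SD 0.6, 0.8 or 1.0, independent of the earlier loss;
- ROTEM cuts later loss by 40%.

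**3. Arithmetic check of one cell (earlier log-SD 0.35, later log-SD 0.8, 50/50).** For a lognormal with median m and log-SD s, mean = m·exp(s²/2) and SD = m·√(exp(s²)(exp(s²) − 1)).
- Earlier loss: SD = 384 mL.
- Later loss, control arm: mean 826 mL, SD 782 mL.
- Difference in means: 0.4 × 826 = 331 mL.
- Average within-arm variance of the total: 384² + 782² × (1 + 0.6²)/2 = 147,456 + 415,836 = 563,292, so SD = 751 mL.
- Standardized difference: 331/751 = 0.44. Power ≈ Φ(0.44/0.2 − 1.96) = Φ(0.24) ≈ 59%. Simulation gives 61%.
- Share of variance from the earlier loss: 147,456/563,292 = 26%. With log-SD 0.1 its SD is 101 mL and the share is 10,201/(10,201 + 415,836) = 2%.

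**4. Simulated power** (several thousand trials per cell; repeat runs agree within about 3 points). Log ANCOVA means log total loss adjusted for log loss at randomization.

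| Earlier log-SD | Groups | Later log-SD | Raw ANOVA | Log ANCOVA | Gain (points) |
|---|---|---|---|---|---|
| 0.35 | 50/50 | 0.6 | 76% | 98% | 22 |
| 0.35 | 50/50 | 0.8 | 61% | 83% | 22 |
| 0.35 | 50/50 | 1.0 | 45% | 63% | 18 |
| 0.35 | 26/23 | 0.6 | 45% | 78% | 33 |
| 0.35 | 26/23 | 0.8 | 32% | 51% | 19 |
| 0.35 | 26/23 | 1.0 | 23% | 34% | 11 |
| 0.1 | 50/50 | 0.6 | 96% | 98% | 2 |
| 0.1 | 50/50 | 0.8 | 77% | 85% | 8 |
| 0.1 | 50/50 | 1.0 | 52% | 65% | 13 |

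**5. Log scale without the covariate (earlier log-SD 0.35).** At 50/50, raw ANOVA 75 / 61 / 45% becomes 76 / 63 / 50%. At 26/23, 45 / 33 / 24% becomes 46 / 35 / 29%. The gain is 1, 2 and 5 points in both, so the covariate does most of the work.

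**6. Smaller effect.** With a 20% cut and earlier log-SD 0.35, 50/50 gives 24 / 18 / 13% raw and 42 / 26 / 18% adjusted. Both are underpowered.

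**7. Other inputs.** Take earlier loss with mean 1200 mL, later loss with mean 400 or 800 mL, and a 30% cut, and analyze log later loss adjusted for log earlier loss. At 50/50 raw ANOVA on the total has 13-67% power and the adjusted analysis 56-99% when the earlier loss has CV 0.3-0.5. When that loss is nearly constant the gain is about 2-12 points.

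**8. No treatment effect.** Raw ANOVA rejects in about 4-6% of trials, and the adjusted analysis stays close to 5%.

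**The case against.** The strongest objection is that the documents give no PPH threshold, no interval from PPH to randomization, and no blood-loss SD or expected effect. If women are randomized close to a common loss, adjustment gains little, and nearly all of that gain comes from the log scale. This stands: the cost is conditional. Against near-constancy, vaginal and cesarean deliveries are pooled, hemorrhage may be managed in the labor room or the operating room, and the moment of randomization is not specified.

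Three further objections also stand in part.
- **Availability.** Recruitment has ended, so no new reading can be taken, and the documents do not say that time-stamped readings were stored.
- **Which measurement.** The endpoint list names a visual estimate as well as EBL, while STUDY PROCEDURES describes a quantitative system. The analysis sentence does not say which one goes into the ANOVA.
- **Skewness.** A reader might infer that right skew is the main fault. Skew is plausible, but no distribution is given, Kruskal-Wallis is allowed in general terms, and step 5 shows that the log scale alone adds little in the main scenario. A rank test does not adjust for earlier loss either.

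A reader might also infer that the total contains everything lost before randomization. The endpoint is intraoperative loss, and labor-room loss in women later moved to the operating room may fall outside it. That some earlier loss is included is a sound inference, not a statement in the text.

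**Conclusion.** The point holds as one about precision. The plan compares blood loss without adjusting for, or separating, loss before randomization, although the sequence of events makes that loss a probable part of the total. Under the main assumptions adjustment is worth about 18-22 points of power at 50/50 and 11-33 at 26/23. With nearly constant earlier loss it is worth about 2-13 points at 50/50.

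It is tempting to conclude that the plan wastes much of the endpoint's power, or that the blood-loss result is invalid. The documents support neither. The first depends on variation they do not report. The second is wrong, because randomization balances earlier loss in expectation and the type I error is held. The endpoint is secondary with no stated power, so no figure in the plan becomes incorrect. The change is worth making, but the trial's main result does not depend on it.

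**What to change.** In BIOSTATISTICAL ANALYSIS, take blood loss out of the ANOVA sentence and add wording such as: *Quantitative blood loss will be analyzed by ANCOVA of log total loss on treatment group, with log cumulative loss at randomization as covariate, taken from the stored time-stamped reading of the running measurement. The result will be reported as a ratio of geometric means with 95% CI.* Name the quantitative measurement explicitly, so that it is not confused with the visual estimate.

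Where no reading at randomization was kept, analyze log total loss and say that this recovers little (about 1-5 points in the main scenario). Report how many women in each arm have a stored reading. Because the trial has closed and its primary result is known, label the adjusted analysis as added afterwards.

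The cost is SAP wording and retrieval of stored readings, with no patient burden. The downsides are that results are ratios instead of mL and that adjustment is limited to women with a stored reading.
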